## Protocol Amendment Summary of Changes

### Protocol History

Version Number	Type	Version Date
1.0	Original Protocol	19-Aug-2020
2.0	Global Amendment to the Original Protocol	28-Jun-2021

### Protocol Version [2.0] (28-June-2021)

### Overall Rationale for the Amendment

Section # and Name	Description of Change	Brief Rationale
Section 1.3. Schedule of Activities; Section 4.2. Scientific Rationale for Study Design; Section 8. Study Assessments and Procedures; Section 8.1.3. COVID-19 Survey; Section 9.4.3. Other Analyses	Addition of a COVID-19 Survey for participants	To collect data on the potential impact of COVID-19 on the study endpoints.
Section 1.3. Schedule of Activities; 8.1. Efficacy Assessments and Procedures; 8.1.5.1. Expanded Disability Status Scale/ CCI	CCI	
Section 8.3.5. Pregnancy	Addition of pregnancy reporting details during the gap period	Details of pregnancy occurring during the gap period need to be collected in the adverse event (AE) page and reported to Global Patient Safety.
CCI		
Throughout	Minor editorial and document formatting revisions	Minor; therefore, have not been summarized.

- Confidential -

This document is the property of Merck KGaA, Darmstadt, Germany, or one of its subsidiaries. It is intended for restricted use only and may not – in full or part – be passed on, reproduced, published or used without express permission of Merck KGaA, Darmstadt, Germany, or its subsidiary. Copyright © 2021 by Merck KGaA, Darmstadt, Germany, or its subsidiary. All rights reserved.

CONFIDENTIAL  
INFORMATION

2/66

Global Version ID: CCI

---

**1 Protocol Summary****1.1 Synopsis**

**Protocol Title:** A 2-year follow-up study to assess cognition and health-related quality of life in participants with highly-active relapsing multiple sclerosis, having participated in the CLARIFY MS trial

**Short Title:** Cognition and HRQoL in adults with highly-active RMS in Year 3 and 4 after initial Mavenclad® dose

**Rationale:** Highly-active relapsing multiple sclerosis (RMS) is characterized by neurological deterioration, causing motor and cognitive dysfunction and impacting health related quality of life (HRQoL). Whilst the randomized control studies on cladribine tablets (Mavenclad®) provide a wealth of information on clinical and safety outcomes, this study will add to the evidence by investigating the long-term effect (over 2 years after initial treatment) on cognition and patient-reported outcomes (PROs) among adults with highly-active RMS.

**Objectives and Endpoints:** The primary and secondary objectives and endpoints are provided in [Table 1](#).

**Table 1 Objectives and Endpoints**

Objectives	Endpoints
Primary	
To assess cognitive impairment in participants with highly-active relapsing multiple sclerosis (RMS), having participated to the CLARIFY MS trial, at 4 years after initial dose of cladribine tablets	Percentage of participants with no or minimal decline in cognitive function, defined as an improved or stable Symbol Digit Modalities Test (SDMT) score or a decline of 4 points or less in the SDMT score, at 4 years after initial dose of cladribine tablets (M48) compared to SDMT score prior to initial dose of cladribine tablets (CLARIFY MS trial Baseline)
Secondary	
To assess health related quality of life (HRQoL) in participants with highly-active RMS, having participated in the CLARIFY MS trial, at 4 years after initial dose of cladribine tablets	
 
Change in HRQoL as measured by the Multiple Sclerosis Quality of Life-54 Questionnaire (MSQoL-54) physical and mental health scores at 4 years after initial dose of cladribine tablets (M48) compared to prior to initial dose of cladribine tablets (CLARIFY MS trial Baseline)
 
Change in HRQoL as measured by MSQoL-54 physical and mental health scores at 4 years after initial dose of cladribine tablets (M48) compared to M24
 

**Substance code: N/A**

**Cognition and HRQoL in adults with highly active RMS in Year 3 and 4  
after initial Mavenclad® dose**

**MS700568\_0158**

---

HRQoL=Health related quality of life; SDMT=Symbol Digit Modalities Test; MSQoL-54=Multiple Sclerosis Quality of Life 54 Questionnaire; RMS=Relapsing Multiple Sclerosis.

**Overall Design:** This is the extension study to the 2-year CLARIFY MS trial to observe participants during the third and fourth year after the initial cladribine tablet dose; no cladribine tablets will be administered during the extension study period. At the extension study Baseline, data will be collected retrospectively from the potential transition gap period between the CLARIFY MS trial and CLARIFY MS Extension study (i.e., between M24 and extension study Baseline). In addition, participants will attend visits for assessments at the extension study Baseline (planned to coincide with or be as near to M24 as possible to minimize the transition gap period), M36 at 36 months/3 years after initial dose of cladribine tablets, and M48 at 48 months/4 years after initial dose of cladribine tablets.

**Disclosure Statement:** This will be an open label, single arm, exploratory, multicenter, retrospective and prospective, 2-year Phase IV study. The purpose of the study is the evaluation of the effect of a treatment for highly-active RMS.

**Number of Arms:** 1

**Blinding:** Not applicable

**Number of Participants:** Depending on the drop-out rate of the parent study, it is expected that up to a maximum of 380 participants will be enrolled into the extension study. Assuming a drop-out rate over the course of the extension study of 10% to 20%, it is expected to achieve a maximum of 300 to 340 evaluable participants for the extension study.

**Study Intervention Groups and Duration:** The extension study will cover a 2-year period in which the participants will not be treated with cladribine tablets, which were administered in the CLARIFY MS trial.

[figure not shown]
**Involvement of Special Committee(s): Yes**

A Steering Committee (SC) will be established; the SC Charter will be in place that describes the SC responsibilities. The SC is a multidisciplinary group of lead study Investigators, medical experts, and Sponsor's personnel, who, collectively, have the scientific, medical, and clinical study management experience to design, conduct and evaluate the study. The SC provides advice and recommendations regarding the design, the conduct, and the evaluation of the study. The SC is responsible for safeguarding the interests of participants and for the conduct of the study.

## 1.2 Schema

A schema of the study design, including both CLARIFY MS (parent study) and CLARIFY MS Extension (extension study), is presented below.

**Figure 1: Study Schema**

Note: M36 and M48 will be planned relative to CLARIFY MS Baseline; a potential delay in M24 (i.e., the Final Study Visit of the CLARIFY MS trial) due to a delay in the initiation of the second-year cladribine tablet treatment does not affect the timing of M36 and M48.

Baseline of the extension study will include retrospective data collection from the potential transition gap (i.e., period between M24 and CLARIFY MS Extension Baseline) and prospective assessments.

## 1.3 Schedule of Activities

The recommended order of the assessments is as provided in the Schedule of Activities ([Table 2](#)).

**Table 2 Schedule of Activities**

Assessments & Procedures	Assessment Period					Notes
	Baseline	M36	End of Study/ M48	Unscheduled Visits	Early Dis-continuation Visit	
Study month (from initial administration of cladribine tablets)	Between CLARIFY MS Final Visit (M24) and M36	36 ± 28 days	48 ± 28 days	24-48		
Visit window						
Informed Consent	X					
Inclusion/exclusion criteria	X					
Demography	X					
Medical history	X					For medical history, only serious adverse events (SAEs) which are ongoing from the CLARIFY MS trial will be recorded (as described in Section 8.3.1)
Concomitant medications and procedures	X	X	X	X	X	Baseline data will be collected retrospectively from the transition gap between CLARIFY MS Final Visit (M24) and CLARIFY MS Extension Baseline for any concomitant medications that may have been initiated in that time period
Cognitive Function						
CCI	[REDACTED]	[REDACTED]	[REDACTED]	[REDACTED]	[REDACTED]	[REDACTED]
HRQoL						
Multiple Sclerosis Quality of Life 54 - Instrument (MSQoL-54)		X	X		X	
CCI	[REDACTED]	[REDACTED]	[REDACTED]	[REDACTED]	[REDACTED]	[REDACTED]
COVID-19 Survey		X	X		X	
Employment Status			X		X	

Assessments & Procedures	Assessment Period					Notes
	Baseline	M36	End of Study/ M48	Unscheduled Visits	Early Discontinuation Visit	
Safety Assessments						
Physical examination		X	X	X	X	
Vital signs		X	X	X	X	
Adverse event reporting	X	X	X	X	X	Baseline data will be collected retrospectively from the transition gap between CLARIFY MS Final Visit (M24) and CLARIFY MS Extension Baseline for any AEs and SAEs that may have occurred in that time period
Disability						
		■	■	■	■	CCI
		■	■	■	■	
		■	■	■	■	
		■			■	
Relapse report	X	X	X		X	Baseline data will be collected retrospectively from the transition gap between CLARIFY MS Final Visit (M24) and CLARIFY MS Extension Baseline for any relapses that may have occurred in that time period
CCI						
CCI		■				CCI

Assessments & Procedures	Assessment Period					Notes
	Baseline	M36	End of Study/ M48	Unscheduled Visits	Early Discontinuation Visit	
CCI						CCI
Patient diary	Continuously					To be filled out by the participant in a continuous manner
CCI ; AE=Adverse event; CCI ; COVID-19=Corona Virus Disease 2019; CCI ; HRQoL=Health related quality of life; CCI ; CCI ; MS=Multiple Sclerosis; MSQoL-54=Multiple Sclerosis Quality of Life 54 Questionnaire; CCI ; SAE=Severe adverse event; CCI						

## 2

## Introduction

Cladribine tablets (Mavenclad®) are approved (European Medicines Agency approval on 25 August 2017) for the treatment of highly-active relapsing multiple sclerosis (RMS) in adults. Detailed information on the chemistry, pharmacology, efficacy, and safety of cladribine tablets is in the Summary of Product Characteristics (SmPC).

### 2.1 Study Rationale

Highly-active RMS is characterized by neurological deterioration causing motor and cognitive dysfunction and impacting health related quality of life (HRQoL) (Jones 2016). Whilst the randomized control studies on cladribine tablets provide a wealth of information on clinical and safety outcomes, there is a call for Phase IV studies to monitor long-term effects of sequential disease-modifying therapies (Derfuss 2020).

This study will add to the evidence by investigating the long-term effect (over 2 years after initiation of treatment) on cognition and patient-reported outcomes (PROs) among adults with highly-active RMS. This extension study will collect 2-year follow-up data to the CLARIFY MS trial till up to 4 years after initial dose of cladribine tablets to explore the long-term effects of cladribine tablet administration.

For further information on study rationale, please refer to Section 4.2.

### 2.2 Background

Multiple sclerosis (MS) is a chronic, inflammatory, progressive, demyelinating disease of the central nervous system and is the most common cause of serious neurological disability in young adults (Przybek 2015). The disease course of MS is heterogeneous and unpredictable requiring chronic treatment and regular medical monitoring by numerous methods such as, magnetic resonance imaging (MRI) that was designed for the investigation, diagnosis and management of patients with MS (Oreja-Guevara 2015).

Some patients experience a highly-active disease course with rapid and early disability often heralded by high relapse rates and early motor, cerebellar and/or cognitive dysfunction (Hirst 2008). Early initiation of effective immunotherapy is considered to be important in this group of patients in order to prevent aggressive disease progression and severe disability accumulation (Dubey 2015).

Despite the recent approvals of several newer therapies, the treatment burden of MS remains significant. While clinical studies demonstrate evidence for the efficacy of new therapies, these studies are often of a limited duration and may not capture long-term outcomes (Lucchetta 2020). Long-term studies are needed to establish the clinical benefits as well as the potential impact on cognitive impairment and HRQoL by new drugs in MS patients.

It has been demonstrated that treatment with cladribine tablets in 2 short courses over 2 consecutive years has consistently shown robust clinically and statistically significant benefits in patients across the spectrum of Relapsing Remitting Multiple Sclerosis (early to late stages, treatment naïve or experienced patients) (Giovannoni 2010; Leist 2014). In particular, it was found that treatment with cladribine tablets resulted in significant improvements in clinical and radiological efficacy

outcomes, with significantly more patients remaining free from relapse, free from 3-month sustained Expanded Disability Status Scale (EDSS) progression, and free from MRI lesion activity over 96 weeks compared to placebo ([Giovannoni 2010](#)).

Efficacy data from the CLARITY trial showed a statistically significant lower annualized relapse rate (ARR), higher proportion of patients relapse-free over 96 weeks, higher proportion of patients free of sustained disability over 96 weeks, and longer time to 3-month EDSS progression in participants receiving cladribine tablets 3.5 mg/kg compared to participants on placebo ([Giovannoni 2010](#)). In addition, cladribine tablets were statistically significantly superior to placebo with regard to numbers and relative reduction of T1 Gd+ lesions, active T2 lesions, and combined unique active (CUA) lesions as demonstrated in brain MRI over the entire 96 weeks of the study ([Comi 2013](#)).

## 2.3 Benefit/Risk Assessment

The primary aim of this study is to assess cognition and HRQoL over the third and fourth year after initial administration of cladribine tablets. Results from this study may be of benefit to patients with MS and clinicians by helping to inform future treatment approaches and treatment decision-making.

The benefit/risk relationship was carefully considered in the planning of this extension study. More detailed information about the known and expected benefits and risks and reasonably expected adverse events (AEs) of cladribine tablets may be found in Section 4.2 and the [SmPC](#). Also, during the CLARIFY MS trial, study participants received cladribine tablets, which were considered to have a positive benefit/risk profile that supported their use in this participant group. Minimal risk to participants is expected since participants enrolled in this study will not be receiving any study treatment; the cladribine tablets treatment course is to be completed under the study protocol of the CLARIFY MS trial, and participants will receive routine clinical care over the extension study period. The CLARIFY MS Extension study will be of an interventional nature, because of the MRI scans, blood draws, and PROs, as per study protocol. These additional diagnostic or monitoring procedures do not pose more than minimal risk or burden to the safety of the participants compared to normal clinical practice.

CCI

Blood draws may cause discomfort, bruising, and very rarely infection at the site where the skin is punctured by the needle. Patients may also experience dizziness, nausea or fainting during blood sampling. However, in general these reactions are mild to moderate and will resolve on their own.

Based on the available clinical and safety data to date, the conduct of the study, as specified in this protocol, is considered justifiable.

### 3 Objectives and Endpoints

The study objectives and their linked endpoints are described in [Table 3](#). For the statistical aspects of the endpoints, refer to [Section 9.4](#).

**Table 3** **Study Objectives**

Objectives	Endpoints
Primary	
To assess cognitive impairment in participants with highly-active RMS, having participated in the CLARIFY MS trial, at 4 years after initial dose of cladribine tablets	Percentage of participants with no or minimal decline in cognitive function, defined as an improved or stable Symbol Digit Modalities Test (SDMT) score a or a decline of 4 points or less in the SDMT score, at 4 years after initial dose of cladribine tablets (M48) compared to SDMT score prior to initial dose of cladribine tablets (CLARIFY MS Baseline)
Secondary	
To assess health related quality of life (HRQoL) in participants with highly-active RMS, having participated in the CLARIFY MS trial, at 4 years after initial dose of cladribine tablets	
 
Change in HRQoL as measured by Multiple Sclerosis Quality of Life 54 Questionnaire (MSQoL-54) physical and mental health scores at 4 years after initial dose of cladribine tablets (M48) compared to prior to initial dose of cladribine tablets (CLARIFY MS Baseline)
 
Change in HRQoL as measured by MSQoL-54 physical and mental health scores at 4 years after initial dose of cladribine tablets (M48) compared to M24
 

CCI	
To assess the long-term (4 years) safety and tolerability of cladribine tablets	
 
Occurrences of adverse events (AEs) and serious adverse events (SAEs) during the third and fourth year after initial dose of cladribine tablets
 

CCI	

Objectives	Endpoints
CCI	

Objectives	Endpoints
CCI	

Objectives	Endpoints

CCI
 
CCI [REDACTED] CCI
 
Visuospatial Memory Test-Revised; CVLT-II=California Verbal Learning Test-II; CCI [REDACTED]; HRQoL=Health related quality of life; CCI [REDACTED] MS=Multiple Sclerosis; MSQoL-54=Multiple Sclerosis Quality of Life 54 Questionnaire; CCI [REDACTED] RMS=Relapsing Multiple Sclerosis; SAE=Serious adverse event; CCI [REDACTED]; CCI [REDACTED]
 
CCI
	

## 4 Study Design

### 4.1 Overall Design

- This will be an open label, single arm, exploratory, multicenter, retrospective and prospective, 2-year Phase IV extension study, of participants with highly-active RMS who completed the CLARIFY MS trial (EudraCT no.: 2017-002632-17).
- The CLARIFY MS trial was a single arm, open label, multicenter, 2-year Phase IV study of participants who received cladribine tablets for 2 years, with one treatment course of 2 weeks at the beginning of each year. The Final Study Visit of the CLARIFY MS trial (M24) is planned 12 months after the initiation of the second-year treatment; initiation of the second-year treatment is planned 12 months after initial dose of cladribine tablets, but could be delayed due to, for instance, lymphocyte count below expected ranges.
- The extension study involves the follow-up of participants for an additional 2-year period (until 4 years after initial administration of cladribine tablets), during which the participants are not treated with cladribine tablets. The aim is to include participants from countries with at least 20 participants enrolled in the CLARIFY MS trial or sites with at least 10 participants enrolled in the CLARIFY MS trial.
- The extension study Baseline will be planned as near to M24 as possible; the extension study Baseline may also be the same visit as M24. At Baseline, data will be collected retrospectively from the potential transition gap period between M24 and CLARIFY MS Extension Baseline, and prospective data will be collected as per Schedule of Activities (Section 1.3). Informed consent for participation in the extension study needs to be obtained before any assessments which are specific to the extension study.
- Participants will attend visits for assessments, including the extension study Baseline, M36 at 36 months/3 years since initial dose of cladribine tablets, and M48 at 48 months/4 years since initial dose of cladribine tablets. The visits should be planned as close to the yearly date as possible, but as a maximum, fall within a window of  $\pm 28$  days. A participant may return for an Unscheduled Visit at the discretion of the Investigator to undergo further evaluations. The data from Scheduled and Unscheduled Visits will be collected in the electronic case report form (eCRF).
- In the event of early discontinuation from the extension study, the participant will be invited to return for the Early Discontinuation Visit for final assessment. In case the participant is not willing to or cannot return to the site for the Early Discontinuation Visit, a telephone call will be organized to obtain the reason for withdrawal and AE reporting.
- The schema and visit schedules for efficacy and safety assessments are detailed in Sections 1.2 and 1.3.
- The study aims to enroll the first participant in Q1 2021 and have the last participant's visit in Q4 2023.
- A Scientific Steering Committee (SC) will be established to ensure that the study meets scientific standards (Refer to [Appendix 2](#)).

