## 5.1 Inclusion Criteria

Participants are eligible to be included in the study only if all the following criteria apply:

1. Participants having participated in the CLARIFY MS trial, who
  - a. Have at least CLARIFY MS Baseline data on SDMT
  - b. Received at least a single dose of cladribine tablets in the CLARIFY MS trial
  - c. Completed the Final Study Visit (M24) of the CLARIFY MS trial.
2. Capable of giving signed informed consent, as indicated in [Appendix 2](#), which includes compliance with the requirements and restrictions listed in the informed consent form (ICF) and this protocol.

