### 9.4 Statistical Analyses

The study is exploratory in nature. A control of the potential Type-I-error inflation caused by multiple endpoints and multiple testing is not implemented.

Parameter estimates with associated 95% confidence intervals will be reported, as applicable.

The study dataset comprises of multiple outcome assessments made for each participant over a 24-month period. Therefore, due to the longitudinal nature of the data and the lengthy follow-up period, it is likely that missing outcome data will be present due to loss to follow-up. Patterns

and degrees of missingness will be summarized and will trigger the approach to deal with missing data.

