#### 9.4.3 Other Analyses

Participants' demographic factors and extension study Baseline clinical characteristics will be summarized.

The data collected with the COVID-19 Survey will be analyzed as additional explanatory variables to the efficacy analyses by possible impacts of the pandemic.

As the extension Study Visits are initiated 2 years after the initial treatment with cladribine tablets, it cannot be excluded that a specific type of participant from the CLARIFY MS trial is available for follow-up. A potential selection bias will be evaluated by comparing the characteristics of the participants from the CLARIFY MS trial and the participants included in this study.

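### Does a late second course undermine the M48-versus-M24 quality-of-life contrast, given that Section 9 speaks of a flat 24 months?

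*Protocol*

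**What the plan says.** Three parts of the protocol fix the timing.

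- Section 4.1: "The Final Study Visit of the CLARIFY MS trial (M24) is planned 12 months after the initiation of the second-year treatment". The second course is itself planned 12 months after the first dose but may start late; a low lymphocyte count is the example given.
- Note to Figure 1: M36 and M48 are counted from CLARIFY MS Baseline, and a late M24 caused by a late second course "does not affect the timing of M36 and M48".
- Table 2 places extension Baseline "Between CLARIFY MS Final Visit (M24) and M36", and Section 5.1 admits only participants who "Completed the Final Study Visit (M24) of the CLARIFY MS trial".

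Table 3 has two secondary MSQoL-54 contrasts. One compares M48 with CLARIFY MS Baseline. The other is the change "at 4 years after initial dose of cladribine tablets (M48) compared to M24". Neither is given a length in months beyond the naming of the visits. Table 6 analyses both with a repeated-measures mixed model, names age and EDSS as examples of adjustment factors, and reports mean differences between the named time points.

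Two sentences in Section 9 use round periods. Section 9.4 describes the dataset as "multiple outcome assessments made for each participant over a 24-month period". Section 9.4.3 opens its remark on selection with "As the extension Study Visits are initiated 2 years after the initial treatment with cladribine tablets".

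**The concern.** Set side by side, the timing rules let one end of the M48-versus-M24 contrast move while the other stays put. A participant with a late second course has a shorter interval between the two visits than one treated on schedule. Section 9.4 nevertheless attributes 24 months to each participant, and Section 9.4.3 dates the start of the extension visits at 2 years.

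If the reported mean difference were read as a uniform two-year change, it would in fact be an average over unequal intervals. Nothing in Table 6 names elapsed time as an adjustment factor. The cause of delay that Section 4.1 mentions is a participant characteristic, so interval length might not be random.

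A similar boundary question arises for safety. The third year after first dose begins at month 24, whereas Section 8.3.1 starts extension recording of adverse events at exit from the parent trial, planned at month 24 + d.

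**Working it through.** **Inputs.** Second course at month 12 + d (Section 4.1; d = 0 when on schedule). M24 is 12 months later (Section 4.1). M48 is at month 48 from first dose, with a window of 28 days either way (Section 4.1, Table 2, Figure 1 note). The protocol does not give d, so the values below are assumptions.

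**The plan's own figure.** M24 = 12 + d + 12 = 24 + d. Interval = 48 - (24 + d) = 24 - d. At d = 0 this is 24 months, as Section 9.4 says.

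**With a delay.**

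| d (months, assumed) | M24 at month | M24 to M48 (months) | Share of 24 |
|---|---|---|---|
| 0 | 24 | 24 | 100% |
| 1 | 25 | 23 | 95.8% |
| 3 | 27 | 21 | 87.5% |
| 6 | 30 | 18 | 75% |
| 12 | 36 | 12 | 50% |

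The last row is a limit, not an expectation. M24 must be complete before entry, and extension Baseline must fall no later than M36, so 24 + d is at most 36 and d at most about 12.

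**Ordinary visit variation.** 28 days = 28/30.44 = 0.92 month. With M24 taken as exact, an undelayed interval is 24 ± 0.92, or 23.1 to 24.9 months. If M24 also varied by 28 days (assumed; the parent protocol is not shown), the half-width is 2 × 0.92 = 1.84 and the range is 22.2 to 25.8. A delay of 3 months gives 21 ± 0.92, or 20.1 to 21.9, in the first case, and 21 ± 1.84, or 19.2 to 22.8, in the second. So it is clear of visit variation in the first case and overlaps it in the second.

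**Effect on the mean interval.** Shortening = share delayed × d. Low end: 0.05 × 1 = 0.05 month, or 0.05/24 = 0.2%. High end: 0.30 × 6 = 1.8 months, or 1.8/24 = 7.5%. Among the 300 to 340 evaluable participants expected, that is 0.05 × 300 = 15 to 0.30 × 340 = 102 people. Shares and delays are assumed. The protocol gives no MSQoL-54 trajectory, so months cannot be turned into score points.

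**What the alternative would cost.** When d is above 0, only one of two intervals can be held fixed.

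| M48 counted from | Baseline to M48 | M24 to M48 |
|---|---|---|
| First dose (as planned) | 48 | 24 - d |
| M24 | 48 + d | 24 |

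The second row would give the M24 contrast a constant length but would move the primary SDMT endpoint and the other MSQoL-54 contrast off 48 months, for example to 54 months at d = 6.

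**The two sentences in Section 9.** The 2 years in Section 9.4.3 run from first dose to the start of the extension visits. That time is 24 + d months at the earliest, and later if extension Baseline follows M24. It is not the length of any contrast. The 24 months in Section 9.4 are the nominal length of the extension and lead into the statement that some outcome data will probably be missing. Neither sentence defines an endpoint, an estimand or a model term.

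**The case for a change.** The strongest case for a change is that Section 9.4 speaks of each participant, so it is literally untrue for anyone whose second course was late, and a separate analysis plan does not correct a sentence in the protocol. The contrast affected is a named secondary endpoint reported with a confidence interval and a p-value, and the varying interval may be related to lymphocyte recovery.

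Part of this stands. The wording of 9.4 is exact only at d = 0. That of 9.4.3 is exact only when, in addition, extension Baseline coincides with M24. Delay may also be linked to participant characteristics; the protocol cannot show whether this matters.

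The rest does not carry a change:

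- A reader of Section 4.1 and Figure 1 is told plainly that the spacing can vary. The contrast is the change between two named visits, and its estimate is the same whatever Section 9.4 calls the period.
- The factors in Table 6 are given as examples, so elapsed time is not excluded. Describing the actual intervals, or adding a supportive analysis, is ordinary content for the Integrated Analysis Plan to which Section 9 refers and which is not at hand. A restriction to participants with an on-time M24 would drop a selected group and could only be supportive.
- Table 2 marks no MSQoL-54 at extension Baseline, but this removes no better reference. That visit is never earlier than M24, so for a delayed participant it falls at month 24 + d or later.
- On safety, no undercount can be shown. Extension recording begins where the parent trial ends, Section 9 allows parent data to be integrated, and the safety row of Table 7 is redacted.

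**Conclusion.** The concern is correct as arithmetic but does not call for a change. For a participant delayed by d months, the M48-versus-M24 MSQoL-54 contrast covers 24 - d months. This follows from an openly stated choice that keeps M48 at four years from first dose. That is a fair trade-off, because it protects the primary endpoint and the other MSQoL-54 contrast, neither of which uses M24.

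What remains is nominal wording in two background sentences of Section 9. Analysts can resolve it from Section 4.1 and Figure 1, and correcting it would change no estimate.

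The size is unknown because the protocol gives neither the frequency nor the length of delays. Under the assumed range of 5% to 30% delayed by 1 to 6 months, the mean interval shortens by 0.2% to 7.5%. Individual intervals can differ by more. The effect is confined to one secondary contrast in a study that calls itself exploratory and applies no control for multiple testing.
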